#### **Patient inclusion**

The number of participants in the cohort will be 0 at day 1 increasing to 400 at 12 months. After month 12 the number of participants will decrease steadily until month 24 where the last patient is finishing the trial. Information and inclusion will be handled by the endoscopist or a research nurse with GCP certificate.

#### **Patient recruitment:**

Patient inclusion is performed at the endoscopic units (Department of Surgery, Odense University Hospital, Södersykehuset, Stockholm, University Hospital, Uppsala, Sahlgrenska Goteborg). All patients undergoing a resection of high-risk adenomas as defined in inclusion criteria at one of the recruiting units will be offered participation if no contraindications are present.

Patient inclusion, flow and randomization procedure: Two scenarios:

### Scenario 1 - Resection at first visit:

Finding and removing high-risk polyp at the current colonoscopy

After performing the colonoscopy, the endoscopist will consider the inclusion and exclusion criteria and if the patient is eligible he/she will be given an oral information about the study (attachment 4 b). All information will be given along with information about the finding from the colonoscopy according to national guidelines in privacy by the endoscopist or the specialized nurse (in a private room with close d doors to ensure patient confidentiality). The patient is informed that he/she has the right to have a person of his own choice to participate. If the person is not there at the moment, the patient can come accompanied after the 48 hour time to think, to a talk at the scheduled location – the information will also be given accordingly to confidentiality guidelines in a private room by an endoscopist or the specialized nurse. The patient will receive written information and informed consent to bring home and will be given at least 48 hours of consideration time before signing it. The patient will call the project nurse if he/she is interested in participating in the study and will not be contacted regarding the clinical study if he/she does not contact us.

If the patient agrees, he/she will come to the facility with informed consent signed and will be instructed by the project nurse and also receive a diary/calendar, questionnaire and 8 liters of juice for 2 months treatment.

### Scenario 2 - Resection at second visit:

Finding and not removing high-risk polyp at initial colonoscopy, following a referral to specialized unit for later removal.

At the first colonoscopy polyp (s) are identified that need referral to EMR/ESD. Patients are informed about the project and informed consent and written info are handed out. All information will be given along with information about the finding from the colonoscopy according to national guidelines in privacy by the endoscopist or the specialized nurse (in a private room with close d doors to ensure patient confidentiality). The patient is informed that he/she has the right to have a person of his own choice to

participate.. When they come back to the specialized unit for resection, earliest 48 hours after the first colonoscopy, the patient will bring the informed consent signed if he wants to participate in the study or if he/she has further questions or needs another person to be present at the discussion, the project nurse will answer the questions and furthermore instruct the patients. If the patients agrees entering the study, they will be handed out 8 liters of carrot juice, diary and questionnaire.

For further information about the recruitment scenarios, see attachment "patient flow".

# **Common pathway**

At the inclusion visit, a compliance diary/calendar will be handed out for registration of compliance and also a basic questionnaire. Patients will be given 2 months juice (8 liters) when included and will be appointed after 2 months to collect another 8 liters of juice in the department. Patients will be informed that they will receive a call after 1 month from each appointment, where their questions and concerns are answered. If the patients need to reschedule the appointment he/she can call at the number that will be written on the information paper or if he/she doesn't show up, the dedicated staff will contact them on the number they wrote in the questionnaire.

Regarding of the recruitment scenario (1 or 2), in order to follow the national guidelines, patients who have had a piecemeal resection will have an additional control colonoscopy at 3 months.

All patients will undergo a full colonoscopy at one year from the moment of the enrollement After the procedure, information about recurrence, the number of polyps, polyp size and characterization will be registered in the database. Polyp size will be measured with the aid of appropriate instruments, like biopsy forceps and slings.

After completing the study period of 1 year, all patients will enter the standard follow up program.

[figure not shown]
Full compliance is defined as consumption of > 75% of the juice delivered. However, because we do not know the minimal effective dose, all participants will be encouraged to continue the study even if they had drop-outs of juice consumption that lead to a < 75% compliance. In addition, participants with incomplete compliance will be registered and included in the study as a sub-group for separate analysis. But the project nurse will assess the patients every 2 months when they pick up the juice and if almost complete non-compliance is registered, the patient will be excluded from the study.

**Randomization:** The study is designed as a double-blinded, randomized controlled study. The randomization is stratified by inclusion center, each having its own block of 50/50 distribution between active and placebo arm. Each unit will receive blocks of juice marked A and B for the active juice or either the placebo juice. The randomization key is generated in the RedCap randomizer. The juice producer holds the key for supplementary delivery to each participant center every 6 months. New shipments are delivered, marked with the same randomization letter.

When the last patient has taken the last dose, the code is broken and patient identity and information of active/placebo juice is combined in the database by an independent staff member.

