### Task1.4 Clinical trial (Lead: OUH. Partners: KUH, UUH, SUH)

We will conduct a prospective double-blinded randomized controlled trial in 1 Danish and 3 Swedish centers. Participants in the intervention arm will receive a daily treatment with 100mL FaOH/FaDOH-rich carrot juice for 1 year. Participants in the placebo arm will receive a daily treatment with 100 mL of placebo juice for 1 year. We will include patients who undergo a resection of high-risk colorectal adenomas, who meets the inclusion criteria at the time of their procedure.

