# Methodology

# Design of the intervention

The trial will be conducted as a double-blind controlled, randomized study. Patients, who, at colonoscopy, had high-risk adenomas, are randomized in 2 arms. One arm will receive 100 ml of carrot juice with a high concentration of falcarinol and falcarindiol daily for 1 year and the other arm will receive 100 ml of placebo juice daily for 1 year until their follow up full colonoscopy. The placebo juice will be produced from commercially available artificial juice without Falcarinol or Falcarindiol. At the follow up colonoscopy, another standardized report will be fulfilled by the endoscoper, containing information about recurrence, the number of polyps, polyp size and risk stratification (no-, low-, medium, high risk polyps or cancer).

The compliance will be registered through diaries/calendars and patients will be followed through the entire period, regardless of their level of compliance. Patients with compliance drop-outs will be encouraged to reenter and complete with as high a compliance as possible.

Patients will be informed that they will receive a call after 1 month from each appointment, where their questions and concerns will be answered.

After the first colonoscopy, patients will be offered inclusion into the trial. If the resection of the high-risk polyp took place in the first colonoscopy, the patient will call the project nurse if he/she is interested in participating in the study and make an appointment for being enrolled in the project. If the resection will take place in a specialized unit where a second colonoscopy will be performed for the resection, then they will give their final answer at this appointment.

The patient will collect 8 liters of juice/placebo every 2 months at a visit at the clinic. At this visit, they will be interviewed for compliance, intake of additional carrots/carrot containing products and possible side effects. If the project nurse assesses the patient as non-compliant then he/she will be excluded from the study.

Each participant will have 6 visits and the 4 institutions will in total have 2400 visits, which is approximately 600 visits in two years at each institution. Visits can be organized in weekly group sessions. Compliance diaries and questionnaires will be explained and collected according to written instructions.

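### Full compliance is measured against juice delivered, which includes a surplus of about 31%; with six deliveries the 75% cut-off amounts to 98.6% of the prescribed volume (82.2% with five)

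*Protocol*

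**What the plan says.** The daily volume is 100 ml in both arms. For the active arm, Task 1.4 (Clinical trial) says "Participants in the intervention arm will receive a daily treatment with 100mL FaOH/FaDOH-rich carrot juice for 1 year", and it gives the placebo arm the same volume and duration.

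The supply is described in three places:

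- Design of the intervention: "The patient will collect 8 liters of juice/placebo every 2 months at a visit at the clinic".
- Scenario 1: "8 liters of juice for 2 months treatment".
- Common pathway: "Patients will be given 2 months juice (8 liters) when included and will be appointed after 2 months to collect another 8 liters".

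On visits, Design of the intervention says "Each participant will have 6 visits and the 4 institutions will in total have 2400 visits". The number of juice deliveries is not stated as such.

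Common pathway sets the cut-off: "Full compliance is defined as consumption of > 75% of the juice delivered". It attributes falling short to "drop-outs of juice consumption that lead to a < 75% compliance", and adds that "participants with incomplete compliance will be registered and included in the study as a sub-group for separate analysis". Among the secondary outcomes, the protocol lists polyp number and size by level of compliance, and compliance itself.

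The protocol does not mention a reserve within the 8 litres, the return or measurement of unused juice, or any adjustment of the denominator to the volume prescribed.

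**The concern.** A compliance ratio should show how much of what was asked for was taken. Here the denominator is what was handed out, and that exceeds what was asked for. Handing out a surplus is not in itself a mistake. Counting it in the denominator is, because a participant who follows the instructions exactly leaves the surplus undrunk and loses points for it. Common pathway presents a score below 75% as the result of missed juice, but the surplus alone uses up almost the whole 25-point margin if there are six deliveries.

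At stake is who counts as fully compliant. With six deliveries, near-perfect takers would be placed with genuine low takers in the sub-group set aside for separate analysis. The reported full-compliance rate would be too low, and any comparison of polyps between compliant and non-compliant participants would be diluted. The meaning of the cut-off also shifts with a delivery count that the definition does not fix.

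**Working it through.** **Inputs**

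- Daily volume: 0.1 L (Task 1.4; Design of the intervention).
- Volume per hand-out: 8 L for two months (Design of the intervention; Scenario 1; Common pathway).
- Visits per participant: 6 (Design of the intervention).
- Cut-off: more than 75% of delivered volume (Common pathway).
- Treatment period: one year, taken as 365 days.
- Number of deliveries: inferred. Hand-outs at months 0, 2, 4, 6, 8 and 10 make six, which matches the six visits. Five is shown as the alternative.

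**The protocol's own figures.** The visit total reproduces: 400 × 6 = 2400, or 2400 / 4 = 600 per institution. The description of 8 L as two months of juice does not. At 0.1 L a day, 61 days need 0.1 × 61 = 6.1 L, and 8 / 6.1 = 1.31, a surplus of 31%. The surplus is 29% for 62 days (8 / 6.2) and 36% for 59 days (8 / 5.9). At this rate 8 L lasts 8 / 0.1 = 80 days.

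**Formulas.** Prescribed volume P = 0.1 × 365 = 36.5 L. Delivered volume D = 8 × number of deliveries. Perfect-intake score = P / D. Cut-off as a share of prescribed = 0.75 × D / P. A participant taking 90% of doses drinks 0.9 × 36.5 = 32.85 L.

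| | Six deliveries | Five deliveries |
|---|---|---|
| D | 48 L | 40 L |
| Perfect-intake score | 36.5 / 48 = 76.0% | 36.5 / 40 = 91.25% |
| Cut-off volume | 0.75 × 48 = 36.0 L | 0.75 × 40 = 30.0 L |
| Cut-off as share of prescribed | 36.0 / 36.5 = 98.6% | 30.0 / 36.5 = 82.2% |
| Doses needed (strictly more than the cut-off) | 361 | 301 |
| Missed days allowed | 365 − 361 = 4 | 365 − 301 = 64 |
| Score of a 90% taker | 32.85 / 48 = 68.4%, fails | 32.85 / 40 = 82.1%, passes |

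**Prescribed volume as denominator.** 0.75 × 365 = 273.75, so 274 doses are needed and 365 − 274 = 91 days may be missed. The two denominators therefore disagree for anyone missing 5 to 91 days with six deliveries, and 65 to 91 days with five.

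**Sensitivity to duration (six deliveries; durations assumed).** At 360 days perfect intake is 36.0 / 48 = 75.0%, which does not exceed 75%, so nobody taking 100 ml a day can qualify. At 375 days it is 37.5 / 48 = 78.1%, and 375 − 361 = 14 missed days are allowed. A 90% taker scores 32.4 / 48 = 67.5% and 33.75 / 48 = 70.3% respectively, and fails in both.

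**Intake above 100 ml (amounts assumed).** The risks section foresees some participants taking more than recommended but gives no amount. With six deliveries and 365 days, a mean of 105 ml on days taken needs 36.0 / 0.105 = 342.9, so 343 days, with 22 missed. A mean of 110 ml needs 36.0 / 0.110 = 327.3, so 328 days, with 37 missed. Drinking more than prescribed thus offsets missed days.

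**The case against.** The strongest objection is that the headline depends on an inferred delivery count. With five deliveries a 90% taker qualifies, and no near-perfect taker is mislabelled. That is right, and the mislabelling should be read as conditional on six. But five deliveries do not repair the definition: the cut-off is then 82.2% of the prescribed volume, still not 75%.

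A second objection is that delivered may be loose wording for the supplied daily doses. Compliance is recorded by diary or calendar, the text speaks of lapses in intake, and nothing is said about measuring leftover juice, so staff may never compute the ratio as written. This is plausible, and it makes the mislabelling a risk under the literal text rather than a certainty. It leads to the same correction, however, because the two readings differ by 87 missed days (91 − 4) with six deliveries.

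Third, credit for intake above 100 ml is not peculiar to this denominator: volume consumed over volume prescribed would credit it too. That stands. It is a side issue that any volume-based score must settle.

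Fourth, the reach is limited. The primary comparison, the exclusion for almost complete non-compliance and an analysis by graded compliance do not use the cut-off. That also stands, and it limits the weight of the point. A statistical analysis plan might fix the derivation, but the protocol already states a definition, and that definition misclassifies if followed.

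**Conclusion.** The concern holds. The definition counts surplus juice as juice that should have been drunk. Under the natural reading of six deliveries over 365 days at 100 ml a day, perfect intake scores 76.0%, the cut-off is 98.6% of the prescribed volume, and the fifth missed day loses the label. Under five deliveries the cut-off is 82.2%.

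The mismatch between the denominator and the prescribed volume follows directly from the protocol's own figures. The mislabelling of near-perfect takers rests additionally on six deliveries and on applying the definition literally. The damage is confined to the full-compliance label, its rate, the incomplete-compliance sub-group and any dichotomised compliance analysis. The point should be corrected, but it does not threaten the primary result.

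**What to change.** - Define compliance as volume or doses consumed, from the diary or calendar, divided by the volume or doses prescribed from first dose to the one-year colonoscopy.
- Choose the analysis cut-off deliberately on that scale. Simply carrying 75% over moves the allowance from 4 to 91 missed days (six deliveries, 365 days). Settle it before the code is broken.
- If delivered volume is kept as the basis, subtract unused juice or reset the cut-off, and state how many deliveries are counted.
- State how intake above 100 ml a day is scored.
- Reconcile the text that calls 8 litres two months of juice with the text giving 100 ml daily, for example by saying whether the 8 litres includes a reserve. Which volume applies is for the investigators to say.

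The cost is one revised definition under Common pathway, one decision on the cut-off and one database derivation. Confirm first that the diary or calendar records daily intake, since the protocol does not describe its content. If it does, no new data are needed.

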#### **Outcome measures**

Primary:

• The primary outcome is the number and size of polyps found at the one-year follow up colonoscopy in the treatment arm and in the placebo arm.

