#### Secondary:

- Number of patients with polyps in the two arms
- Polyp number and size in relation to level of compliance to treatment.
- Risk stratification of polyps identified at follow up in each arm.
- Number of polyps with low, medium and high degree of dysplasia and cancer.
- Compliance, side effects and acceptability of treatment.
- User preference of carrot intake across patient profiles and carrot products.

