# Data collection, management and analysis

Data will be collected after informed consent will be obtained. Patients will be informed that researchers involved in the project will have access to their data and in need (control or inspection purposes), sponsors and regulatory authorities will have access to our database.

The consent provides the responsible researcher, sponsor, investigator, and their representatives, as well as any regulatory authority, direct access to obtain information in the patient's medical records, including electronic records, for the purpose of reviewing information related to the subject's health status that is necessary for the conduct of the research project and for monitoring purposes, including self-monitoring, quality control, and monitoring tasks that they are obligated to perform.

Data collection will be performed by dedicated research staff. Data will be collected and entered into the electronic database REDCap via OPEN at OUH. We will enter data from the questionnaire, patient journal, pathology answer etc.

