### Information collected from patient files and questionnaires:

From the patient file: Quality and technical details of both colonoscopy, allergies, former colonoscopies and polypectomies and the pathology report on adenomas resected. Only data necessary to answer the described aims will be collected.

We will not need to give patient information to others to recruit patients. The patients will be invited to participate if they have a polyp bigger than 20 mm regardless of other information from the patient journal which we will not access at this timeline. Patient information will not be collected at the inclusion but will be accessed by research responsible and entered into a RedCap database after the patient will be already included in the project. Only project members have access to data and data will be destroyed after analysis. The project will be registered in the Data Protection Agency. The data protection law and regulations will be obeyed including the chapter V.

Data obtained in Sweden will be entered into the Danish RedCap database in OPEN directly after a data sharing agreement has been lawfully obtained between the sites. After the completion of the database all data will be pseudoananomized. Data will be destroyed after publication of the results from the 3-year colonoscopy, or – if scientifically useful, prolongation until the 5-year colonoscopy will be applied for.

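### The code is broken at the last patient's last dose, so unblinding can precede the last colonoscopy and the completion of pathology, compliance and outcome data

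*Protocol*

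**What the plan says.** The Randomization paragraph of the Protocol (under Common pathway) times the code break as follows: "When the last patient has taken the last dose, the code is broken". At that moment an independent member of staff brings patient identity and arm together in the database.

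Other sections fix when the outcome data arise:

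- Design of the intervention has juice taken up to the colonoscopy: "the other arm will receive 100 ml of placebo juice daily for 1 year until their follow up full colonoscopy".
- Outcome measures: "The primary outcome is the number and size of polyps found at the one-year follow up colonoscopy".
- Design of the intervention, on the follow-up colonoscopy: "another standardized report will be fulfilled by the endoscoper, containing information about recurrence, the number of polyps, polyp size and risk stratification".
- Common pathway: "After the procedure, information about recurrence, the number of polyps, polyp size and characterization will be registered in the database".
- Data collection, management and analysis: "We will enter data from the questionnaire, patient journal, pathology answer etc".
- Information collected from patient files and questionnaires lists "the pathology report on adenomas resected" among the items taken from the file.
- The secondary outcomes include "Number of polyps with low, medium and high degree of dysplasia and cancer", and also relate polyp findings to compliance.

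No section makes the code break wait for any of these steps. Completion of the database is mentioned once, in the section on information from patient files, and there only as the point for pseudonymisation.

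**The concern.** The unblinding rule is tied to treatment, but the data to be protected are generated at or after the end of treatment. Once arm sits beside patient identity in the database, whoever enters or cleans an open record with access to that database could know the allocation.

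The steps still open may involve judgement: transcribing pathology, settling queries, and placing a participant above or below the 75% compliance limit. For a late or postponed colonoscopy, the endoscopist's own assessment of polyps could also be made after the code break. Even if no bias occurs, the sponsor could not show that the data were final before unblinding.

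**Working it through.** The Protocol gives no figure for this point, so there is none to reproduce. The check is the order of events, followed by simple counts.

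**Order of events for the last participant**

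| Step | Source in the Protocol | Relation to the code break |
|---|---|---|
| Last dose | Randomization | Is the trigger |
| One-year colonoscopy | Outcome measures; Design of the intervention | At or after the trigger, since juice runs until the procedure |
| Registration of findings | Common pathway | After the procedure, so after the trigger |
| Pathology entered | Data collection; Information collected from patient files | After the procedure, so after the trigger |
| Final diary and compliance data | Design of the intervention; Common pathway | Cannot be complete before the last dose |

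The colonoscopy is anchored to enrolment (Common pathway), not to the last dose. Participants are also followed whatever their compliance (Design of the intervention). A postponed colonoscopy, or juice stopped early among the last participants, therefore widens the gap.

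**Primary outcome.** The endoscopist reports polyp number, size and risk class at the colonoscopy, so for nearly all participants this precedes the code break. The last participant may be an exception:

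- of the planned 400 (Sample size): 1/400 = 0.25%
- of the minimum 328 completers (Sample size): 1/328 = 0.30%

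Anyone whose colonoscopy falls after the trigger date is additional. The wording makes this possible, not certain.

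**Compliance.** Juice is collected every two months over one year: 12/2 = 6 intervals. For the last finishers, at most the final interval, 1 of 6, is open.

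**Pathology and data entry.** The number of open records is the finishing rate times the lag. Patient inclusion has participants finishing steadily over months 12 to 24, about 52 weeks:

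- all 400 finish: 400/52 = 7.7 per week
- 80% finish, allowing for the stated 20% drop-out (0.80 × 400 = 320): 320/52 = 6.2 per week

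The Protocol gives no turnaround for pathology or data entry, so I give the rate per week of lag and no total.

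**Time available.** The Time schedule ends observation in January 2026 and plans publications before January 2027, an interval of about 11 to 12 months.

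**The case against.** The strongest reply is that the practical effect is slight. Under the planned schedule, last dose and last colonoscopy nearly coincide. The trigger is a single trial-wide date, so almost every colonoscopy has by then been reported blind. This stands, and it is why the primary-outcome exposure is put at about one participant plus late procedures. The dates in the Time schedule do not prove a longer gap either, because slower inclusion would move last dose and colonoscopy together.

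Second, nothing suggests that the grading pathologist sees the trial database, so what clearly remains open is entry of an existing report. That also stands: the secure claim concerns data entry, not biased grading. Similarly, compliance rests on diaries with a numeric limit, and no later intake can be influenced once the last dose is taken. What remains is late collection and classification for the last finishers.

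Third, an independent person does the linking. This settles who acts, not when, and the result goes into the database that holds the outcomes.

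Fourth, database lock is commonly left to an SAP or data management plan. That would answer a silence, but the Protocol states its own trigger. A later date elsewhere would contradict it.

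**Conclusion.** The point holds. As written, the Protocol permits unblinding before the last one-year colonoscopy and before pathology, final compliance data and outcome entry are complete.

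The likely effect on the primary result is small: 1 of 400 (0.25%) or 1 of 328 (0.30%), plus any colonoscopy after the trigger date. The main exposure lies in pathology-based secondary outcomes, the compliance sub-group and data cleaning. There, about 6 to 8 records are open per week of lag. That rate assumes steady finishing and an unstated turnaround; it counts open records and does not estimate bias.

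The wording should be corrected, because a double-blind trial should have its data final before arm is known. It does not invalidate the design.

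**What to change.** Replace the code-break sentence in the Randomization paragraph with wording such as:

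> The code is broken only after the last participant's one-year colonoscopy findings, pathology results and final compliance data have been entered and the database has been locked. An independent staff member then attaches the allocation to the locked data.

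This keeps the independent staff member and changes only the trigger. It alters no treatment or clinical rule.

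The cost is one sentence and a short delay in unblinding. The length depends on a turnaround the Protocol does not give, but about 11 to 12 months between the end of observation and planned publication are available to absorb it.
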